Subjects in the study are those:

- who have at least a 3 month history of 3-14 migraines, with or without aura, as defined by International Classification of Headache Disorders (ICHD) -3 beta (Appendix 1) or treat with a ergot or triptan and received relief.
- who received a diagnosis of migraine before age 50.
- who have used acute headache medication 14 or fewer days per month in the previous 3 months.

STUDY MEDICATION

Subjects will receive Investigational Drug Product MLD10 as follows: 2 MLD10 caplets, oral, twice daily or placebo caplets as follows: 2 placebo caplets, oral, twice daily.

BACKGROUND & STUDY RATIONALE

Magnesium is frequently used in the treatment and prevention of migraine, though there are relatively few clinical trials supporting its efficacy. While there is a sound scientific rationale for magnesium as a migraine preventative, different forms of magnesium differ significantly in their solubility and bioavailability. In addition, there are challenges in measuring bioactive magnesium levels in the body. Consequently, a discussion of the efficacy of magnesium needs to be specific to the formulation of magnesium being studied, its ability to be adequately absorbed, and physiologically active.

Magnesium is recognized to block the N-methyl-D-aspartate ion-dependent channel. Low levels of magnesium increase the sensitivity of the NMDA receptor to glutamate. Glutamate is an excitatory neurotransmitter and is considered central to the development of cortical spreading depression. In addition, glutamate is considered to play an excitatory role in the hyper-vigilant migraine nervous system. Thus, magnesium properly utilized physiologically has significant potential to protect the nervous system from migraine.

PRIMARY OBJECTIVE

To compare the change from baseline to treatment period months 1, 2, and 3 in the number of migraine headache days of subjects treated with MLD10 versus placebo.

SECONDARY OBJECTIVES

To compare change from baseline of subjects treated with MLD10 versus placebo on the following parameters during a 3 month treatment period:

- the number of headache days
- the average headache duration
- pain severity at headache onset
- the use of acute medications
- Migraine Disability Assessment Scale (MIDAS) scores
- Subject Global Impression of Change (SGIC)
- Physician Global Impression of Change (PGIC)

EXPLORATORY OBJECTIVES

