- Severity of headache at the time of onset (mild, moderate, or severe) only for subjects who report a headache duration > 0)
- Acute headache pain medication(s) usage
- Study medication usage
- Unusual symptoms

Should a subject skip a day of e-diary entry, the subject will be able to provide the missing information for up to 1 calendar day. The e-diary should not be completed on the day of the office visit; the last e-diary entry for the preceding period should be completed the day prior to the office visit.

Questionnaire data required to be directly collected from subject will be obtained at each appropriate visit using an electronic device as defined in the protocol. Questionnaires are to be completed by the subject and the answers to the questions on the questionnaires should come from the subject directly, not from family, friends, or the study support personnel.

Questionnaire data required to be collected directly from clinicians will be obtained at the appropriate visit and recorded in the eCRF per protocol.

STATISTICAL ANALYSIS

Subjects will be randomized 1:1 into the treatment groups. Randomization will not include any type of stratification.

An alpha of .05 will be used for statistical significance. All statistical tests will be two-sided. All data will be analyzed using JMP (SAS Institute, Inc.).

Descriptive statistics will establish baseline characteristics and adverse event frequency. Data for the primary endpoint will be statistically analyzed via a repeated measures ANCOVA controlling for ionized serum Mg levels. Data for each of the secondary outcome measures will be statistically analyzed for both within and between group changes via a 2-tailed Repeated Measures ANOVA and/or independent or dependent t-tests as appropriate. All ANOVAs will be followed by univariate post-hoc tests as appropriate. Multiple comparison adjustments will be made if needed.

An interim analysis will be performed when approximately 60 subjects have completed the study. The results of the interim analysis may lead to stopping the study for safety or futility. The interim analysis will not lead to stopping the study for efficacy. Only the primary endpoint and first secondary endpoint of migraine and headache day reduction will be assessed at the time of the interim analysis, as well as adverse events for safety purposes.

Modified Intent-to-Treat Population (mITT)

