The modified intent-to-treat (mITT) population will include all randomized subjects who received at least one dose of study drug and obtained at least one endpoint measurement (mean change from baseline in the number of hours with headaches) after treating. The mITT population will be used for efficacy analyses.

Safety Population

The safety population will include all randomized subjects who received at least one dose of study drug (active or placebo).

A last observation carried forward (LOCF) method will be utilized to impute missing values for subjects continuing in the study, but missing values for this analysis. This type of imputation replaces the missing value with the last observation value obtained. Baseline observation carried forward (BOCF) method will be used if a subject discontinues the study. Thus, if a subject has a missing value at month 2 due to discontinuation, the baseline value will be utilized and the subject will be considered a non-responder.

PRIMARY ENDPOINT

To compare the mean change from baseline in the frequency of migraine headache days per 28-day period ending with the cessation of treatment period month 3 in subjects treated with MLD10 versus placebo.

A migraine headache day will be defined as a calendar day (00:00 to 23:59) with 4 or more hours of migraine headache, fulfilling ICHD-3 beta criteria, and/or any headache of any duration with the use of migraine-specific acute medications(s) (i.e. ergot alkaloids, ergot combinations, opioids, triptans, combination analgesics [simple analgesics combined with opioids or barbiturate with or without caffeine]).

SECONDARY ENDPOINTS

1. To compare change from baseline of subjects treated with MLD10 versus placebo on the following parameters during or after a 3 month treatment period:
 - the frequency of headache days
 - the average headache duration after 1, 2, and 3 months of treatment
 - reduction of pain severity at the time of headache onset
 - the use of acute medications after 1, 2, and 3 months of treatment
 - Migraine Disability Assessment Scale (MIDAS) scores at Visits 2 and 5
 - Subject Global Impression of Change (SGIC) at Visit 5
 - Physician Global Impression of Change (PGIC) at Visit 5
2. To assess the safety and tolerability of magnesium-L-lacate-dihydrate versus placebo in migraine headache subjects through the comparison of adverse events.

EXPLORATORY ENDPOINTS

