To compare the change from baseline of subjects treating with MLD10 versus placebo on the following parameters during a 3 month treatment period.

- migraine with aura days
- serum ionized magnesium

SAFETY ENDPOINTS

Safety assessments will include:

- adverse events

COLLECTION AND DERIVATION OF ENDPOINTS

Data required for the evaluation of endpoints will be recorded for the duration of the study using electronic data capture and included subject and clinician reported outcomes.

Following visit 2, subsequent visits will occur every 28 days for 3 months. However, in practice, there may or may not be an exact 28-day duration between 2 consecutive visits. For data analysis purposes, the number of migraine headache days during the first 28 continuous days of the run-in period will serve as the “baseline” for calculating change from baseline for 28-day periods subsequent to each office visit. If the run-in period (starting with the screening visit and preceding the day before visit 2) exceeds 28 days, the run-in period will include the last 28-days. In order to be randomized, a subject must meet 80% diary completion compliance (22 days recorded unless otherwise approved by the Sponsor and/or Clinvest).

Primary Efficacy Variable

The primary efficacy variable is the mean change from baseline in the frequency of migraine headache days per 28-day period ending with the cessation of treatment period month 3 in subjects treated with MLD10 versus placebo. This variable is derived from

the e-diary. It is based on the count of days with migraine headaches, fulfilling ICHD-3 beta criteria, and/or headaches of any duration with the use of migraine-specific acute headache medication(s). The primary time point is treatment month 3, encompassing the last 28-day period before study end.

Secondary Efficacy Variables

- Change from baseline in the frequency of headache days per 28-day period. This variable will be derived from daily e-diary reports. It will be based on the count of days with headaches.
- Change from baseline in the total cumulative hours of headache per 28-day period. This variable will be derived from daily e-diary reports. It will be based on the sum of total headache duration for days with any headache.
- Change from baseline in the average pain severity at time of onset compared to each 28-day period. This variable will be derived from the daily e-diary reports.

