- Reduction from baseline in the total number of acute headache pain medications used. This variable will be derived from the daily e-diary reports.
- Change from baseline in the total MIDAS score. This variable will be derived from the subject questionnaire.
- SGIC score at the end of treatment. This variable will be derived from the subject questionnaire.
- PGIC score at the end of treatment. This variable will be derived from the clinician reports.

APPENDIX 1
Proposed Revised International Headache Society Criteria for
Migraine Without and With Aura

Headache Classification Committee: J Olesen, et al. The International Classification of Headache Disorders, 3rd edition (beta version). *Cephalalgia*. 2013, 33:629-808.

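### Secondary endpoints defined as MLD10 versus placebo are also to be tested within each arm, and the named between-arm methods do not adjust for the baseline already collected

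*Protocol*

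**What the plan says.** The Statistical Analysis section of the protocol states that each secondary outcome will be "statistically analyzed for both within and between group changes via a 2-tailed Repeated Measures ANOVA and/or independent or dependent t-tests as appropriate". The same section sets the error level for everything: "An alpha of .05 will be used for statistical significance", and "All statistical tests will be two-sided". It does not rank the within-group and between-group results, and it does not call the within-group results descriptive.

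The questions themselves are between-arm questions. Secondary Objectives reads "To compare change from baseline of subjects treated with MLD10 versus placebo on the following parameters during a 3 month treatment period", and Secondary Endpoints reads "To compare change from baseline of subjects treated with MLD10 versus placebo on the following parameters during or after a 3 month treatment period".

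Under Secondary Efficacy Variables, five of the seven efficacy secondaries are changes from baseline: headache days, headache hours, pain severity at onset, acute medication use and MIDAS. The first is "Change from baseline in the frequency of headache days per 28-day period". The other two have no baseline, for example "SGIC score at the end of treatment"; PGIC is defined in the same way.

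For the primary endpoint the plan does name a covariate model: "Data for the primary endpoint will be statistically analyzed via a repeated measures ANCOVA controlling for ionized serum Mg levels". No covariate is named for any secondary.

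**The concern.** A dependent t-test in the MLD10 arm asks whether subjects on MLD10 changed over time. In a placebo-controlled trial of a fluctuating condition they may well change whether or not the drug works. For the diary frequency endpoints, regression to the mean may add to this. Randomization requires at least 3 migraine days in the run-in, and the run-in also supplies the baseline. The eligibility range has an upper limit of 14 days as well, so the net direction is not certain. MIDAS, onset severity and headache hours have no entry threshold of their own.

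Because the within-arm tests are planned at the same alpha, and nothing marks them as descriptive, a significant change on MLD10 could be reported as a secondary result alongside, or instead of, the comparison that the objectives ask for.

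The second issue is smaller. Repeated measures ANOVA and the independent t-test on change subtract the baseline but do not adjust for it. Adjustment usually gives a tighter between-arm estimate from the same data and corrects for chance baseline imbalance, which matters more when randomization is unstratified, as here.

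**Working it through.** **The plan's own figure.** The protocol gives no sample size or power for the secondaries, so the only figure to reproduce is the one in Power Analysis: 128 subjects for 80% power, raised to 142 for 10% dropout. A noncentral F test with 1 numerator degree of freedom, two groups, noncentrality N·f² and f = 0.25 gives N = 128 with power 0.801. Then 128/0.9 = 142.2, in line with 142. The figure reproduces when the printed .25 is read as Cohen's f, which is a standardized mean difference of 0.50. The label is a separate matter. Here it only supplies n = 64 per arm and d = 0.50 as a reference point.

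**Within-arm test when the drug does nothing.** Inputs: n = 64 per arm (128/2), two-sided alpha 0.05. Assumption: both arms improve by the same amount s, in SDs of the change. The protocol gives no placebo response, so s is shown as a range. The paired t statistic has 63 degrees of freedom and noncentrality s·√64 = 8s. Let p be the probability of significant improvement in one arm. Significance on MLD10 but not on placebo then has probability p(1 − p), because a significant worsening is negligible here.

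| s (assumed) | 8s | Significant on MLD10, p | Significant on MLD10, not on placebo | Between-arm test |
|---|---|---|---|---|
| 0.2 | 1.6 | 0.35 | 0.23 | 0.05 |
| 0.3 | 2.4 | 0.66 | 0.23 | 0.05 |
| 0.4 | 3.2 | 0.88 | 0.10 | 0.05 |
| 0.5 | 4.0 | 0.98 | 0.02 | 0.05 |

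The between-arm rate stays at 0.05 because the true difference between arms is zero whatever s is. With all 71 randomized per arm, p is 0.70 at s = 0.3 and 0.99 at s = 0.5, so the picture does not change.

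**Between-arm test with and without baseline adjustment.** Assume equal unit variances at baseline and follow-up and correlation ρ between them. The protocol gives no ρ.

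- Variance of the change score: 2(1 − ρ).
- Residual variance with baseline as covariate: 1 − ρ².
- Ratio: (1 − ρ²)/[2(1 − ρ)] = (1 + ρ)/2.

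Start from a change-score comparison with d = 0.50 and 64 per arm. Its normal-approximation power is Φ(0.50·√32 − 1.96) = Φ(0.868) = 0.81. Adjustment raises the standardized difference to 0.50/√ratio.

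| ρ (assumed) | Ratio (1 + ρ)/2 | Adjusted d | Power after adjustment |
|---|---|---|---|
| 0.3 | 0.65 | 0.620 | 0.94 |
| 0.5 | 0.75 | 0.577 | 0.90 |
| 0.7 | 0.85 | 0.542 | 0.87 |

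This applies to a two-time-point change score. It fits MIDAS directly, since MIDAS is taken at Visits 2 and 5 only and the group-by-time test of a two-point repeated measures ANOVA is the same as the t-test on change. For the monthly diary endpoints it describes a single-month change-score comparison. It does not quantify a repeated measures ANOVA across months.

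**The case against.** The strongest reply is that the protocol never says a within-arm p-value will count as efficacy. Every statement of purpose is MLD10 versus placebo, and the between-group analysis is planned for each secondary. A reader might infer from the within-group tests that the plan counts placebo response as evidence. The text does not support that. What stands is narrower: significance tests are planned that do not address the stated objective, and nothing says how they are to be read.

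Relatedly, the 66% to 98% figures are not false-positive rates for any stated objective. They are the power of a paired test to detect a real change over time. With a placebo arm present, a reader would expect to see a similar change there. The more misleading pattern, significance on MLD10 alone, occurs in about 23% of trials at 0.3 SD and 2% at 0.5 SD. This is right, and it limits the size of the problem without removing it.

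A reader might also infer that baseline is left out of the secondary analyses. It is not: five of the seven efficacy secondaries subtract it, and SGIC and PGIC have none. Under randomization both the change score and the adjusted analysis are unbiased, so the issue is precision and chance imbalance.

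Finally, the choice of test per endpoint and the covariates are commonly settled in a statistical analysis plan, which was not available here. The open wording on which test applies would therefore be no finding by itself. But the within-group tests and the unadjusted methods are stated in the protocol, not left blank, and an analysis plan that follows the protocol would inherit them.

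**Conclusion.** The point holds in a limited form. The protocol plans within-arm significance tests for endpoints it defines as comparisons with placebo, and does not mark them as descriptive. Under no drug effect and an assumed equal improvement of 0.3 to 0.5 SD of change, such a test is significant on MLD10 in about 66% to 98% of trials with 64 per arm, against 5% for the between-arm test.

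The named between-arm methods also forgo a gain in precision: a variance ratio of 0.65 to 0.85 for ρ from 0.3 to 0.7, or about 94% to 87% power where the change score gives about 80%. A reader might turn this into a claim that the secondaries are underpowered. The documents do not support that, because no secondary has a power target to fall short of.

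The improvement sizes and correlations are assumptions. The primary analysis and the sample size are not affected by this point.

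**What to change.** Amend the secondary-analysis sentence in Statistical Analysis as follows:

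- For headache days, headache hours, onset severity, acute medication use and MIDAS, base inference only on the between-arm difference from a model with that endpoint's own baseline value as covariate.
- For SGIC and PGIC, use a plain between-arm comparison of the end-of-treatment score.
- Report within-arm changes descriptively, with confidence intervals and no p-values.

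The cost is wording only. The diary baseline comes from the run-in and the MIDAS baseline from Visit 2, so no new data, visits or subjects are needed.

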1.1 Migraine without aura

Description:

Recurrent headache disorder manifesting in attacks lasting 4-72 hours.

Diagnostic criteria:

- A. At least five attacks¹ fulfilling criteria B–D
- B. Headache attacks lasting 4-72 hours (untreated or unsuccessfully treated)
- C. Headache has at least two of the following four characteristics:
 - 1. unilateral location
 - 2. pulsating quality
 - 3. moderate or severe pain intensity
 - 4. aggravation by or causing avoidance of routine physical activity (e.g. walking or climbing stairs)
- D. During headache at least one of the following:
 - 1. nausea and/or vomiting
 - 2. photophobia and phonophobia
- E. Not better accounted for by another ICHD-3 diagnosis.

1.2 Migraine with aura

Description:

Recurrent attacks, lasting minutes, of unilateral fully reversible visual, sensory or other central nervous system symptoms that usually develop gradually.

Diagnostic criteria:

- A. At least two attacks fulfilling criteria B and C
- B. One or more of the following fully reversible aura symptoms:
 - 1. visual
 - 2. sensory
 - 3. speech and/or language
 - 4. motor
 - 5. brainstem
 - 6. retinal
- C. At least two of the following four characteristics:
 - 1. at least one aura symptom spreads gradually over \geq 5 minutes, and/or two or more symptoms occur in succession
 - 2. each individual aura symptom lasts 5-60 minutes
 - 3. at least one aura symptom is unilateral
 - 4. the aura is accompanied, or followed within 60 minutes, by headache
- D. Not better accounted for by another ICHD-3 diagnosis, and transient ischemic attack has been excluded.

APPENDIX II
Proposed Revised International Headache Society
Criteria for Medication-Overuse Headache

Headache Classification Committee: J Olesen, et al. The International Classification of Headache Disorders, 3rd edition (beta version). *Cephalalgia*. 2013, 33:629-808.

Description:

Headache occurring on 15 or more days per month developing as a consequence of regular overuse of acute or symptomatic headache medication (on 10 or more, or 15 or more days per month, depending on the medication) for more than 3 months. It usually, but not invariably, resolves after the overuse is stopped.

General comment:

In the criteria set out below for the various subtypes, the specified numbers of days of medication use considered to constitute overuse are based on expert opinion rather than on formal evidence.

Diagnostic criteria:

- A. Headache occurring on 15 days per month in a patient with a pre-existing headache disorder
- B. Regular overuse for >3 months of one or more drugs that can be taken for acute and/or symptomatic treatment of headache
- C. Not better accounted for by another ICHD-3 diagnosis.
